### **WEEK 3 (WASHOUT)**

• T1 – Day 15 (+3 days)

All procedures below are completed for research only.

Concomitant Medications of Interest

Current medications of interest will be abstracted through medical record review at T1 visit.

- TNSc Physician or Nurse Assessed
- o TUG
- Questionnaires (can be emailed, mailed, or given in person)
  - FACT/GOG-NTX v4, Neurotoxicity Subscale
  - PROMIS-29
  - ESAS
- Sock Diary Submission Patients will be asked to submit their daily sock diaries to the coordinator.
- Sock Return Patients will be asked to return all study socks to the study coordinator.
- Sock Dispensing Patients will be given 6 new pairs of socks, according to assigned arm:
  - Patients on Arm A will be given 6 pairs of placebo socks along with a start date on when the patient should begin wearing the socks (start date = Day 29). Patients will be asked to wear the socks continuously during both waking and sleeping hours for two weeks from that start date, except when showering, bathing, or swimming.
  - Patients on Arm B will be given 6 pairs of Voxx HPT socks along with a start date on when the patient should begin wearing the socks (start date = Day 29). Patients will be asked to wear the socks continuously during both waking and sleeping hours for

- two weeks from that start date, except when showering, bathing, or swimming.
- Patients will be reminded that the socks can be washed on delicate cycle and worn repeatedly. Patients will be reminded not to let others wear the socks during the course of the trial.
- The investigator and patient will be blinded to treatment assignment.
- Daily Sock Diary Instruction Patients will be reminded to keep a
  daily record of approximately how many hours the socks were worn
  and to note whether the socks were worn while sleeping.

### **WEEK 4** (WASHOUT)

• Day 28 – One Day before Crossover Treatment Start Date (-2 days)
A phone call will be made to the patient to remind them to start wearing their socks the following day (Day 29), and to keep daily records of approximately how many hours the socks were worn.

### WEEK 5

- Continuous Sock Wearing
- Daily Sock Diary Entries
- Reminder Calls

Phone calls will be made to the patients on Day 31(+/- 2 Days) and Day 35(+/-2 Days) to remind the patients to wear their socks and to monitor for any adverse events. Thereafter, patients will be able to call a study coordinator with any questions or concerns.

### WEEK 6

- Continuous Sock Wearing
- Daily Sock Diary Entries

Any patient who stops study treatment early will be encouraged to return to the study center for all study visits. The reason(s) for any study or assessment discontinuation will be documented.

### 6.2.3 T2 (End of Treatment Visit) – Week 7, Day 43 (+3 days)

All procedures below are completed for research only.

- Concomitant Medications of Interest
   Current medications of interest will be abstracted through medical record review at T2 visit.
- TNSc Physician or Nurse Assessed
- TUG
- Questionnaires (can be emailed, mailed, or given in person)
  - FACT/GOG-NTX v4, Neurotoxicity Subscale
  - o PROMIS-29
  - o ESAS
- Sock Return Patients will be asked to return all study socks to the study coordinator.
- Sock Diary Submission Patients will be asked to submit their daily sock diaries to the coordinator.

Time and Events Table

	Screening	T0 (Baseline) within 2 weeks of treatment start date		·	Treatment	rent		*11		Cross	Crossover Treatment	atment	T2* (End of Treatment Visit)
Day			0	1	3	2 8	8-14	15	28	29 31	1 35	36-42	43
Week				1	  -	  -	2	3	4	5 2	2	9	7
Informed Consent	×					 	$\vdash$			L	L		
Medical History	×			Г	Г	H	Н			L	L	L	
Concomitant Medications of Interest	×	×		Г	Г	H	Н	×		L	L	L	×
Pain Assessment (Self-Report)	×			Г	H	H	H			L	L	L	
Assessment of Eligibility	×			Г	Г	L	Н		Г	L	L		
Demographics Questionnaire		×		Γ	┢	H	┝			L	L	L	
TNSc (Physician or Nurse Assessed)		×				L	$\vdash$	×	_	L	L		×
TUG		×		Γ	F	L	H	×	Г	L	L	L	×
FACT/GOG-NTX – Neurotoxicity Subscale		×						×					×
PROMIS-29		×			H	L	Н	×		L	L	L	×
ESAS		×				_		×					×
Socks Dispensed to Patients		×		_		_		×					
Socks Returned by Patients				_		_		×					×
Treatment Implementation				Contir	Continuous Sock Wearing; See Section 6	ck Weari tion 6	.Bc:	WASHOUT PERIOD	TUC OC	Continuc	Continuous Sock Wearing; See Section 6	Wearing; າ 6	
Sock Diary Entries					Daily Entries	ıtries	Н		П	Ö	Daily Entries	ses	
Sock Diary Submission							Н	×	Н		L		×
Patient Reminder Phone Calls			×		×	×			××	×	×		
Adverse Event Monitoring					×	×	Н	Н		×	×		

\*Time point has a +3 day window ^Day 0 and Day 28 reminder calls have a -2 day window X $^1$  Day 3, Day 7, Day 31 and Day 35 reminder calls have a  $\pm 2$  day window

### 6.4 Removal of Subjects from Study

Patients can be taken off the study at any time at their own request, or they may be withdrawn at the discretion of the investigator for safety, behavioral or administrative reasons. The reason(s) for discontinuation will be documented and may include:

- 6.4.1 Patient voluntarily withdraws;
- 6.4.2 Patient withdraws consent (termination of study participation);
- 6.4.3 Patient is unable to comply with protocol requirements;
- 6.4.4 Treating physician judges continuation on the study would not be in the patient's best interest.

### 7.0 ADVERSE EVENTS

### 7.1 Adverse Event Monitoring

Adverse events are extremely unlikely as a result of participation in this study. Patients will be monitored for signs of sock-related skin irritation or discomfort. Only adverse events related to the study intervention will be recorded and reported. Adverse event data collection and reporting, which are required as part of every clinical trial, are done to ensure the safety of Subjects enrolled in the studies as well as those who will enroll in future studies using similar interventions. Adverse events are reported in a routine manner at scheduled times during a trial. Additionally, certain adverse events must be reported in an expedited manner to allow for optimal monitoring of patient safety and care.

All patients experiencing an adverse event related to the intervention will be monitored until:

- the adverse event resolves or the symptoms or signs that constitute the adverse event return to baseline;
- there is a satisfactory explanation other than the study intervention for the changes observed; or
- death.

### 7.2 Definitions

### 7.2.1 Definition of Adverse Event

An adverse event (AE) is any untoward medical occurrence in a patient receiving study treatment and which does not necessarily have a causal relationship with this treatment. An AE can therefore be any unfavorable and unintended sign (including an abnormal laboratory finding), symptom, or disease temporally associated with the use of an experimental intervention, whether or not related to the intervention. For this study, patients will only be monitored for AEs related to study intervention.

The only expected AEs for this study are:

- Skin irritation on the foot or ankle
- Foot/ankle discomfort
- Temporary mild increase of pain in the foot during the first 3 days of sock wear.

### 7.2.2 Severity of Adverse Events

All non-hematologic adverse events will be graded according to the NCI Common Terminology Criteria for Adverse Events (CTCAE) version 5.0. The CTCAE v5 is available at

https://ctep.cancer.gov/protocoldevelopment/electronic applications/docs/CTCA E v5 Quick Reference 5x7.pdf

If no CTCAE grading is available, the severity of an AE is graded as follows:

Mild (grade 1): the event causes discomfort without disruption of normal daily activities.

Moderate (grade 2): the event causes discomfort that affects normal daily activities.

Severe (grade 3): the event makes the patient unable to perform normal daily activities or significantly affects his/her clinical status.

Life-threatening (grade 4): the patient was at risk of death at the time of the event.

Fatal (grade 5): the event caused death.

### 7.2.3 Serious Adverse Events

A "serious" adverse event is defined in regulatory terminology as any untoward medical occurrence that:

### 7.2.3.1. Results in death.

If death results from (progression of) the disease, the disease should be reported as event (SAE) itself.

### 7.2.3.2. Is life-threatening.

(the patient was at risk of death at the time of the event; it does not refer to an event that hypothetically might have caused death if it were more severe).

- 7.2.3.3. Requires in-patient hospitalization or prolongation of existing hospitalization for ≥ 24 hours.
- 7.2.3.4 Results in persistent or significant disability or incapacity.
- 7.2.3.5 Is a congenital anomaly/birth defect
- 7.2.3.6 Is an important medical event

Any event that does not meet the above criteria, but that in the judgment of the investigator jeopardizes the patient, may be considered for reporting as a serious adverse event. The event may require medical or surgical intervention to prevent one of the outcomes listed in the definition of "Serious Adverse Event". For example: allergic bronchospasm requiring intensive treatment in an emergency room or at home; convulsions that may not result in hospitalization; development of drug abuse or drug dependency.

### 7.3 Steps to Determine If an Adverse Event Requires Expedited Reporting

Step 1: Identify the type of adverse event using the NCI Common Terminology Criteria for Adverse Events (CTCAE v5).

Step 2: Grade the adverse event using the NCI CTCAE v5.

Step 3: Determine whether the adverse event is related to the protocol therapy Attribution categories are as follows:

- Definite The AE is clearly related to the study treatment.
- Probable The AE is likely related to the study treatment.
- Possible The AE *may be related* to the study treatment.
- Unrelated The AE is clearly NOT related to the study treatment.

Note: This includes all events that occur within 30 days of the last dose of protocol treatment. Any event that occurs more than 30 days after the last dose of treatment and is attributed (possibly, probably, or definitely) to the agent(s) must also be reported accordingly.

Step 4: Determine the prior experience of the adverse event.

Expected events are those that have been previously identified as resulting from administration of the agent. An adverse event is considered unexpected, for expedited reporting purposes only, when either the type of event or the severity of the event is not listed below:

- Skin irritation on the foot or ankle
- Foot/ankle discomfort

### 7.4 Safety Reporting Requirements

### 7.4.1 Reporting to the Principal Investigator

The Principal Investigator (PI) must be notified by study staff or co-investigators within 24 hours of learning of any SAEs, regardless of attribution and expectedness, occurring during the study or up until the end of treatment visit.

### 7.4.2 Reporting to DSMC

Serious Adverse Events deemed to be related to the protocol and on-study deaths, including death of a research subject unless the death is expected (e.g. due to disease progression) are to be reported to the DSMC within 24 hours of awareness. Hardcopies or electronic versions of the MedWatch Form 3500A (Mandatory Reporting) or a narrative report, along with any other supporting documentation available, should be submitted to the DSMC Coordinator. The DSMC Coordinator will forward the information to the DSMC Chair, and/or medical monitor. The DSMC Chair will review all documentation upon receipt from the DSMC Coordinator and determination of whether the following actions are required: 1) takes action immediately, 2) convenes a special DSMC session (physical or electronic), or 3) defers the action until a regularly scheduled DSMC meeting. Reports are to be emailed to the DSMC team at [contact].

### 7.4.3 Reporting to the Device Manufacturer

Serious Adverse Events deemed to be related to the protocol and on-study deaths, including death of a research subject unless the death is expected (e.g. due to disease progression) are to be reported to the Device Manufacturer within 24 hours of awareness. This will be done via a narrative email.

### 7.4.4 Reporting to the Institutional Review Board (IRB)

As per the Cedars-Sinai IRB Reporting Possible Unanticipated Problems Involving Risks to Subject or Others (UPIRSO) Policy, the IRB must be notified of all UPIRSOs as soon as possible, but no later than 10 business days from when the study team learned of any of the following events:

- 1. Any internal SAE, AE or Research-Related Subject Injury (RRSI), which in the opinion of the Principal Investigator was unanticipated or unexpected, and has a reasonable possibility of relationship to the research.
- 2. Any actionable external SAE, AE, SUSAR, development safety update report (DSUR), or FDA MEDWATCH report deemed to be a UPIRSO. An event is considered "actionable" if it warrants a change to the conduct of the study.
- 3. Any internal or external UADE.
- 4. Any accidental, unintentional protocol or consent/HIPAA related deviation that may impact subjects' rights, safety, or welfare. See section 10.8.3.
- 5. Any planned protocol exception or eligibility waiver. See sections 10.8.2 and 10.8.3.
- 6. Changes to the research or protocol deviations made without prior IRB approval in order to eliminate apparent immediate hazard to a research subject..(Note: These must be reported to the IRB within 5 business days.)
- 7. Problems, events, unanticipated incidental findings, billing problems, or other events, outcomes, or new information related to the research (e.g., publication, safety monitoring report, interim findings, product labeling changes, findings generated from preclinical, animal studies) that may adversely affect the rights, safety, or welfare of the subjects or others, put subjects or others at increased risk, compromise the research data, or require/recommend changes to the study conduct.
- 8. Subject complaints or concerns that cannot be resolved by the research staff to the subject's satisfaction.
- 9. Breach or potential breach of confidential or sensitive information.
- 10. Incarceration of a subject who is enrolled in a study that is not approved by the IRB to include prisoners.

### 7.5 Unblinding Procedures

Unblinding will occur when all data has been entered into the database for all participants and the team has declared the study dataset to be complete. Emergency unblinding will only occur when knowledge of the investigational product is essential for the safety of the patient. The investigator will document in the patient's source document and provide an explanation for any premature unblinding (e.g., accidental unblinding, unblinding due to serious adverse event). Unblinding will be reported to the IRB at the time of annual Continuing Review unless it occurs as part of managing a UPIRSO and then will be reported along the same timelines as the UPIRSO.

### **8.0 STATISTICAL CONSIDERATIONS**

**Sample size and randomization:** This is a pilot crossover study to collect data on effect sizes for the outcomes. Patients will be randomized to one of two treatment sequences as Voxx socks then placebo socks, or placebo socks then Voxx socks. We will enroll 30 patients to allow for dropout to obtain 20 evaluable patients.

**Statistical Methods:** The fundamental analytic approach will be based on a within-subjects comparison of the main outcome measured with Voxx socks versus that measured on placebo in this crossover trial. The primary approach will used linear mixed models with time and treatment effects, adjusted for the repeated measures of subjects nested within sequence in the correlation structure. Carry-over effects will be tested by examining the interaction between treatment and period. In the unlikely event of a statistically significant carry over effect, only data from the first period will be used for the analysis. The overall type I error rate for the primary outcome measure will be controlled at 5%. The main outcome is the score on the Functional Assessment of Cancer Therapy/Gynecologic Oncology Group — Neurotoxicity (FACT/GOG-NTX) Neurotoxicity Subscale.

Data will first be assessed for reliability and general integrity (e.g., distribution characteristics) to ensure that appropriate statistical techniques are applied. Our basic approach to the analysis assumes there are no carry-over effects between the two treatment periods. All subjects entered into the trial will be included in the analysis. Strictly speaking, this is not an "intent-to-treat" policy because the crossover design should assure that each participant receives both Voxx socks as well as placebo in the appropriate treatment periods. If a study participant did not receive one or both treatments, they cannot be included in the primary analysis because that analysis relies on within-subject differences between the treatments. The status of all participants will be reported in the analysis as in the CONSORT recommendations. The fundamental analytic approach will be based on a within-subjects comparison of the relevant outcome measured on Voxx socks versus that measured on placebo. Secondary endpoints will be analyzed the same way as the primary endpoint.

For all secondary objectives, a significance level of 0.05 will be used. A patient will be considered to have completed treatment if they have completed FACT/GOG-NTX at baseline, both treatment periods, and at least 50% compliance for both treatment periods. Compliance will be defined as wearing the socks for at least 16 hours per day.

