### 5.2 Method of Assigning Subjects to Treatment Groups

Study participants will be randomized 1:1 to the two treatment arms of the study in random block sizes of 4 and 6 subjects. Randomization will occur after patients' study eligibility has been confirmed.

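### Switching to first-period data after a significant carry-over test lifts the primary test's type I error above the 5% that the plan promises

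*Combined protocol and SAP*

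**What the plan says.** Everything is in Section 8.0 (Statistical Considerations). The main analysis is within-patient: "The primary approach will used linear mixed models with time and treatment effects, adjusted for the repeated measures of subjects nested within sequence". A preliminary test follows: "Carry-over effects will be tested by examining the interaction between treatment and period". Its consequence is: "In the unlikely event of a statistically significant carry over effect, only data from the first period will be used for the analysis". The next sentence promises that "The overall type I error rate for the primary outcome measure will be controlled at 5" per cent. The section also states: "Our basic approach to the analysis assumes there are no carry-over effects between the two treatment periods".

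The documents give no significance level for the carry-over test, no adjusted level for the first-period test, and no other allowance for a choice of analysis that depends on the data. Section 8.0 applies the same method to the secondary endpoints, so each of those scales can trigger its own switch.

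**The concern.** This is the two-stage crossover procedure. The interaction that it tests is the difference between the two sequences in patients' totals over both periods. Those totals contain the period 1 scores, and the fallback test uses only the period 1 scores. If the sequences differ by chance in period 1, the carry-over test tends to be significant and so does the fallback test. The switch therefore selects the trials in which the first-period comparison is misleading, and then tests that comparison at the full 5%.

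Three things are at stake:
- The stated 5% error rate is not delivered.
- In the fallback branch the trial gives up its within-patient comparison and reports an estimate selected for being extreme. That is a poor result for a pilot meant to supply effect sizes.
- The pre-test is a between-patient test in about 20 people. A non-significant result says almost nothing about whether the no-carry-over assumption is true.

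**Working it through.** **Inputs**
- Target error 5% (Section 8.0). Two-sided testing is assumed because sidedness is not stated.
- Sample size: "We will enroll 30 patients to allow for dropout to obtain 20 evaluable patients" (Section 8.0), with 1:1 allocation (Section 5.2). This gives n = 10 per sequence, or 15 if all 30 are evaluable.
- Pre-test level a: not stated, so 5% and 10% are both shown.
- Within-patient correlation ρ: not stated, so 0.3 to 0.9 is shown.
- Normal scores with SD 1 and the same correlation between T0, T1 and T2: assumed.

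**Step 1: the plan's own figure.** In simulation (100,000 trials per scenario, t tests, no treatment effect, no carry-over), always using the two-period within-patient test rejects in 4.9% to 5.1% of trials. So 5% is obtained when there is no switch.

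**Step 2: how the three tests are related.** Let Y1 and Y2 be a patient's scores at T1 and T2. Each test compares the two sequences.

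| Test | Based on | Variance of the contrast |
|---|---|---|
| Crossover treatment effect | (Y1 − Y2)/2 | (1 − ρ)/n |
| First period only | Y1 | 2/n |
| Carry-over pre-test | Y1 + Y2 | 4(1 + ρ)/n |

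Sums and differences are uncorrelated, so the pre-test is independent of the crossover test. Its correlation with the first-period test is (1 + ρ)/√(2(1 + ρ)) = √((1 + ρ)/2), which is 0.81 at ρ = 0.3 and 0.97 at ρ = 0.9.

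**Step 3: overall error of the procedure.** Let q be the probability that the first-period test rejects given that the pre-test has rejected (bivariate normal). Then

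overall error = (1 − a) × 0.05 + a × q.

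At ρ = 0.7 and a = 0.05: 0.95 × 0.05 + 0.05 × 0.638 = 0.0475 + 0.0319 = 7.9%.

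| ρ | Formula, a = 5% | Simulation, 20 patients, a = 5% | Simulated q, a = 5% | Simulation, 20 patients, a = 10% |
|---|---|---|---|---|
| 0.3 | 7.0% | 6.9% | 43% | 7.6% |
| 0.5 | 7.4% | 7.3% | 51% | 8.0% |
| 0.7 | 7.9% | 7.9% | 62% | 8.6% |
| 0.9 | 8.7% | 8.7% | 78% | 9.2% |

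With 30 patients and a = 5% the range is 6.9% to 8.6%, so more patients do not help. The ceiling at a = 5%, reached as q approaches 1, is 0.0475 + 0.05 = 9.75%.

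**Step 4: use of the baseline score.** Section 2.3.1 defines the endpoint as a change, while Section 8.0 says "The main outcome is the score on the Functional Assessment of Cancer Therapy/Gynecologic Oncology Group", so it is unclear how T0 enters. With 10 per sequence and a = 5%, change from T0 gives 7.1% to 7.5% and T0 as a covariate gives 6.7% to 7.3%. The values of q are about 50% to 52% and 39% to 51%. No variant gives 5%.

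**Step 5: precision lost in the fallback.** The variance ratio, first period to crossover, is (2/n) ÷ ((1 − ρ)/n) = 2/(1 − ρ). This is 2.9, 4.0, 6.7 and 20 at ρ = 0.3, 0.5, 0.7 and 0.9. With T0 as a covariate in the first-period analysis it is 2(1 + ρ), which is 3.0 at ρ = 0.5 and 3.4 at ρ = 0.7.

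**Step 6: what the pre-test can detect.** A carry-over of λ biases the crossover estimate by λ/2, so a bias of one standard error means λ = 2√((1 − ρ)/n). Dividing by the pre-test's standard error, 2√((1 + ρ)/n), gives a signal of √((1 − ρ)/(1 + ρ)): 0.73 at ρ = 0.3 and 0.23 at ρ = 0.9. Power is then 6% to 11% at the 5% level, and 11% to 18% at the 10% level.

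**The case against.** The strongest case is about weight. This is a pilot to gather preliminary data, with no power claim. Under the null hypothesis the switch fires in about 5% of trials (10% with a 10% pre-test), and the excess error is about 2 to 4 percentage points. The largest figures (8.7% overall, 78% in the fallback) need unadjusted scores and ρ = 0.9; with T0 in the analysis the excess is about 2 points. All of this is fair. The 43% to 78% rate is conditional on an uncommon event and should be read that way. But the overall figures already allow for how seldom the switch fires, the excess is present in every variant, and the plan itself chose to claim 5%.

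The fallback might also include more than 10 patients per arm. Section 8.0 excludes patients who missed a treatment because the analysis needs within-patient differences, and that reason does not apply to a first-period comparison. With 15 per arm in the fallback against 10 in the crossover, the variance ratio at ρ = 0.7 would be 6.7 × 10/15 = 4.4. The error rate would still exceed 5%.

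Finally, dropping the switch restores 5% only if there is no carry-over. With a carry-over of 0.5 SD, ρ = 0.7 and 20 patients, always using both periods rejects a true null in about 28% of trials. The present rule does much the same (28% with a 5% pre-test, 27% with a 10% pre-test), since it detects that carry-over only about 9% or 16% of the time. So the switch gives little protection, but its removal does not replace a reasoned case for the washout.

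**Conclusion.** The concern holds. As written, Section 8.0 does not control the primary type I error at 5%. With no treatment effect, no carry-over and 10 patients per sequence, the error is about 6.7% to 8.7% with a 5% pre-test, across ρ from 0.3 to 0.9 and the three ways of using T0. On raw scores with a 10% pre-test it is 7.6% to 9.2%. These figures assume two-sided tests, normal data and equal variances; the pre-test level and ρ are assumed ranges because the documents give neither. The inflation is moderate. It should nevertheless be corrected, because it affects the primary test, contradicts the plan's own next sentence, and comes from a step that adds almost no protection against carry-over.

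**What to change.** Amend Section 8.0 before unblinding (Section 7.5):

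1. Delete the switch to first-period data.
2. State that the two-period linear mixed model, with period, treatment and patients within sequence, is the primary analysis whatever the carry-over result, and say how the T0 score enters it.
3. Report the treatment-by-period contrast as an estimate with a 95% confidence interval, with no decision attached.
4. If a first-period analysis is wanted, label it as sensitivity only and adjust it for T0.
5. Add the reason for taking carry-over to be negligible after the washout. Sections 3.0 and 5.1 give its length without a rationale, and the primary analysis depends on it.
6. Apply the same rule to the secondary endpoints, so that all outcomes rest on the same design.

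If the switch is kept, either withdraw the 5% claim or set a stricter, pre-specified level for the first-period test that holds the overall error at 5%. That is second best, because the fallback estimate would still be selected for being extreme.

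The cost is a few sentences of text. No extra patients, visits or data are needed.

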### **5.0 TREATMENT PLAN**

### 5.1. Treatment Administration

Patients will be randomized 1:1 to one of the following regimens:

- Arm A: Continuous wear of Voxx HPT Socks for 2 weeks, followed by continuous wear of placebo socks for 2 weeks (separated by a 2-week washout period)
- Arm B: Continuous wear of placebo socks for 2 weeks, followed by continuous wear of Voxx HPT Socks for 2 weeks (separated by a 2-week washout period)

Voxx HPT Socks are commercially-available, FDA-exempt compression socks that are drug and electrical free. The Voxx HPT proprietary pattern is woven into a sock that is made of 70% cotton, 25% polyester, 3% spandex, and 2% nylon. Placebo socks will be made of the same fabric and will be identical in appearance to the HPT socks.

Prior to each 2-week treatment window, patients will be provided with 6 pairs of Voxx HPT socks or placebo socks. The investigator and patient will be blinded to treatment assignment between Voxx HPT first versus placebo first.

Patients will be asked to wear the socks continuously during both waking and sleeping hours, except when showering, bathing, or swimming. The socks should only be worn by the patient and should not be shared with other members of the household.

Both the Voxx HPT Socks and the placebo socks can be washed on delicate cycle and worn repeatedly.

Patients will be asked to keep a daily record of approximately how many hours the socks were worn, and whether the socks were worn while sleeping.

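### Does the crossover analysis need a FACT/GOG-NTX score at the end of the washout (Day 28)?

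*Combined protocol and SAP*

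**What the plan says.** Each sequence has two weeks in one type of sock and two weeks in the other; for Arm A, Voxx socks are "followed by continuous wear of placebo socks for 2 weeks (separated by a 2-week washout period" (Section 5.1). Section 6.2 and the Time and Events Table place the subscale at T0, at T1 on Day 15 (+3 days) and at T2, "Week 7, Day 43 (+3 days". At the end of washout the only contact is a call: "A phone call will be made to the patient to remind them to start wearing their socks the following day (Day 29". The table's footnote adds "Day 0 and Day 28 reminder calls have a -2 day window". At T1 the forms need no visit: "Questionnaires (can be emailed, mailed, or given in person".

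Section 8.0 gives the purpose: "This is a pilot crossover study to collect data on effect sizes for the outcomes". On carry-over it states three things. The assumption is "Our basic approach to the analysis assumes there are no carry-over effects between the two treatment periods". The check is "Carry-over effects will be tested by examining the interaction between treatment and period". The consequence is that a significant result restricts the analysis to period 1. No SD, correlation, target effect or power is given.

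**The concern.** T1 falls at the start of the washout and T2 after the second treatment period, so the trial never observes whether the two sequences have come back together before the second socks go on. The documents give no data for a 2-week washout. Section 1.2 mentions an unpublished study in diabetic neuropathy with a decrease after 1 week of use, but says nothing about how long an effect lasts once the socks come off.

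The planned check is a between-patient comparison and has little power with about 20 patients. If part of the Voxx effect persists in Arm A into the placebo period, the effect size that the pilot is meant to supply is too small. An emailed 11-item form at the existing Day 28 contact seems a cheap way to look, and its interval appears much narrower than that of the planned test.

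**Working it through.** The plan has no power or precision figure to reproduce, so results are in SD units.

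**Inputs.** From the documents: 20 evaluable patients and 1:1 allocation, hence about 10 per sequence; last period-1 wear day, Day 14; Day 28 call made on Day 26-28; T2 on Day 43 (+3). Assumed: a common SD of 1, equal correlation r of 0.5 to 0.8 between visits, two-sided 5%.

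**Precision and power.** For a between-sequence contrast with per-patient variance V, SE = √(2V/10) and half-width = t × SE. Here t = 2.101 (18 df) without T0 and 2.110 (17 df) with T0. Power is from the noncentral t.

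| Contrast | V | SE, r = 0.5 / 0.8 | Half-width | Power at 0.25 SD | at 0.5 SD | at 1.0 SD |
|---|---|---|---|---|---|---|
| T1+T2, unadjusted | 2(1+r) | 0.775 / 0.849 | 1.63 / 1.78 | 6% | 9% | 20-23% |
| T1+T2, given T0 | 2+2r−4r² | 0.632 / 0.456 | 1.33 / 0.96 | 7-8% | 12-18% | 32-54% |
| Day 28, given T0 | 1−r² | 0.387 / 0.268 | 0.82 / 0.57 | 9-14% | 23-42% | 68-94% |

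The Day 28 interval is narrower: the T0-adjusted T1+T2 interval is 1.63 to 1.70 times as wide. Simulation with fitted regressions gives slightly lower Day 28 power: 22.8% and 40.0% at 0.5 SD, and 65.2% and 92.3% at 1.0 SD (r = 0.5 and 0.8). These figures assume every Day 28 form comes back. With 75% returned at random, the half-width is 1.02 SD (r = 0.5) or 0.70 SD (r = 0.8).

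**What biases the estimate.** Let d be the Voxx effect and c the fraction still present at T2 in Arm A. The mean of T1−T2 is d − cd in Arm A and −d in Arm B, period effects aside. Half the difference is d(1 − c/2). Recovery is 87.5% at c = 0.25 and 75% at c = 0.5. The relevant c is that at Day 43, 29 days after the last scheduled wear day, and not that at Day 28, which is 14 days after.

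**Linking the two days.** As an illustration, assume exponential decay from Day 14.
- Half left at Day 28: 0.5^(29/14) = 0.238 at T2; recovery 1 − 0.238/2 = 88%.
- A quarter left at Day 28: 0.25^(29/14) = 0.057 at T2; recovery 97%.
- For c = 0.5 at T2, the fraction at Day 28 would have to be 0.5^(14/29) = 0.72.

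**Size against noise.** The half-width of the planned treatment estimate is ½ × √(2−2r) × √(2/10) × 2.101 = 0.47 SD at r = 0.5 and 0.30 SD at r = 0.8. Take d = 0.5 SD with half of it left at Day 28. The loss is 0.5 × 0.238/2 = 0.06 SD, well inside that interval. The Day 28 residual would be 0.25 SD, which the form would detect 9-14% of the time. If the whole 0.5 SD were still there at Day 28, it would be detected 23-42% of the time.

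**What would change in the analysis.** Nothing. The mixed model, the carry-over test and the fallback would all run as written. The fallback's T1 comparison precedes any carry-over. With T0 as covariate its variance is also 1−r², so its half-width is the same 0.57 to 0.82 SD.

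**The case for a change.** The strongest argument is that the planned test is very weak: at most 9% power at a 0.5 SD carry-over and 20-23% at 1.0 SD, because Section 8.0 does not say that T0 enters the model. A Day 28 reading would be more sensitive at trivial cost, would show a very large residual (68-94% power at 1.0 SD), and might guide the washout of a later trial.

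The schedule facts, the weakness of the test and the lack of data behind the 2-week washout all stand. The precision comparison is not like-for-like: one interval is for carry-over at Day 43, the other for a residual at Day 28. They share a scale only if the residual persists unchanged for another 15 days. If it decays, a Day 28 difference could be visible while T2 is hardly affected, and so could mislead about the estimate it was meant to support. Conversely, ±0.6 to ±0.8 SD around zero could not rule out that a whole 0.5 SD effect had persisted. One imprecise reading at one time is also thin evidence for choosing another trial's washout.

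The cost is small but not nil: a protocol amendment with IRB approval, pursuit of unreturned forms, and no data from patients already past Day 28. Whether testing for carry-over and then falling back on period 1 is a good rule is a separate question, which a Day 28 form would not settle.

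**Conclusion.** The concern does not hold. The plan has a washout, states its assumption openly, and says how it will be tested and what follows. No number, rule or analysis is wrong because the subscale is not scored on Day 28. The estimate is unbiased if no effect persists to T2, and the extra score would neither correct it nor govern it. Adding the form is an optional choice on which statisticians could reasonably differ; without it, the missing end-of-washout score can be noted as a limitation when effect sizes are reported.

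The figures rest on 10 patients per sequence, a common SD and equal correlations of 0.5 to 0.8, none of which the documents supply beyond the 20 evaluable patients and 1:1 allocation. Unequal correlations move them: the T0-adjusted T1+T2 half-width is 1.52 SD if T0 correlates 0.5 with later scores and T1 with T2 at 0.8. The decay calculation illustrates why the two days differ and does not estimate how long any effect lasts. If an effect did not fade at all, c would be 1 and the planned contrast would recover half of it. The conclusion that the plan contains no error does not depend on these assumptions.
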